5.3 Counting failures

A screening failure is defined as those participants who agree to participate in the study, giving their consent, but who are not assigned to the treatment group, i.e., do not enter the study. It is necessary to report at least the following information on counting failures:

- Demographics.
- Details of the failure to count (specify whether it is due to eligibility criteria, which one, or some other reason for the failure).
- Presence of serious adverse events during the count.

This is necessary to comply with the CONSORT (*Consolidated Standards of Reporting Trials*) guidelines for the publication of results or to respond to possible questions from regulatory authorities.

5.4 Recruitment and retention strategies

The duration of the subject's participation in the study is approximately 13 days, during which time the subject will be required to attend three visits in total and will be given a safety call, which corresponds to the baseline visits, visit 1, final visit and safety call. Strategies to improve subject retention include, but are not limited to:

- Clearly inform the objectives of the study.
- Make calls or send text messages to remind you of appointments or activities to do.
- Provide a printed calendar and an identification card in order to remember appointments and activities that will be carried out, in addition to the estimated time of their duration.
- Systematic organization of the study procedures, so that the subject does not last longer than necessary in his visit.
- Minimize subject wait times.

All materials to be delivered to the subject or recruitment strategies implemented by the center will be submitted for approval by the corresponding committees.

5.5 Procedure in case of loss of follow-up

For this protocol, loss of follow-up is defined as those subjects who were assigned the PI, who at some point were active subjects of the study, but their final evaluation could not be completed.

In the event that the subject does not terminate their participation due to withdrawal of consent or major deviation, the last visit, in which their withdrawal was determined, will be considered their final visit. Subjects who are removed due to the presence of AEs will continue with the follow-up that is defined until the closure of their AE.

In cases where the participating subject does not attend their appointment, the research center must make a call to find out the reason and will try to make a new appointment within the established window period or an unscheduled appointment. In the event that it is not possible to make an appointment, the subject will be considered as loss of follow-up and will be asked about the presence of adverse events and the reason for leaving the study, as minimum data.

A loss of follow-up <20% is considered not to be a problem for the validity of the results obtained.
[20, 21]

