5.2 Criteria for elimination and/or substitution of subjects

5.2.1 Elimination Criteria

- Withdrawal of the consent form under information.
- Presentation of a serious adverse event, whether or not related to the PIs, that, in the judgment of the PI and/or the sponsor, could affect the patient's ability to continue with study procedures safely.
- Non-tolerability or hypersensitivity to any of the compounds used during the tests (fluorescein, tetracaine).
- No tolerability or hypersensitivity to any of the investigational drugs.
- Adherence < 80% determined by the subject's diary and corroborated by the final weight of the PI with respect to the initial weight.

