7.4.4.3.4 Lagrimeo

Excessive tear production or flow. [35, 36]

The subject will respond only if the symptom is absent or present

These symptoms will be analyzed as one of the variables of the study and will not be considered an adverse event.

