7.4.4.7 Eye Comfort Index

It is a questionnaire designed to measure ocular surface irritation with Rasch analysis to produce estimates on a linear interval scale (ratings: 0-100). Similar to the index for ocular surface diseases, the ocular comfort index (ICO) assesses symptoms. The ICO contains 8 items (one positive and eight negative) that focus on discomfort associated with ocular surface alterations. Each of these questions has two parts, which separately inquire about the frequency and severity of symptoms. [\[43\]](#) See attachment [16.4 Eye Comfort Index \(JI\)](#)

At the baseline visit and final visit, the evaluator will deliver the questionnaire to the subject and allow the subject to answer it calmly without any pressure and/or coercion, only assisting him if he has difficulty understanding any of the questions.

As it is a subjective measurement scale according to the subject's symptomatology, variations in the ICO cannot be managed as AEs.

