7.7.5 Unscheduled follow-up visits

At the request of the subject or personnel related to the study, unscheduled follow-up visits may be carried out for the reporting of adverse events or any situation that warrants it. During these visits, all pertinent data on the adverse events reported should be collected and, where appropriate, an appropriate management plan should be established.

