10.4.1 Procedure for handling missing data

There is no imputation procedure for missing data.

11. Ethical considerations

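### The protocol does not clearly require an ICO or further follow-up for a subject eliminated for not tolerating the drops, and counts such removals in no outcome, so the primary tolerability comparison can miss the least tolerant subjects

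*Combined protocol and SAP*

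**What the plan says.** - **Removal.** The elimination criteria in 5.2.1 include "No tolerability or hypersensitivity to any of the investigational drugs".
- **Follow-up after removal.** Section 5.5 says: "Subjects who are removed due to the presence of AEs will continue with the follow-up that is defined until the closure of their AE". It gives no matching instruction for a removal that is not due to an AE.
- **What may be an AE.** Section 7.4.4.7 says that "variations in the ICO cannot be managed as AEs". Section 7.4.4.3.4 says of burning, foreign body sensation, pruritus and tearing that they "will not be considered an adverse event". Section 7.4.4.6, however, names burning, foreign body sensation and pruritus among the ocular adverse events that can occur with PRO-231.
- **When the ICO is taken.** "At the baseline visit and final visit, the evaluator will deliver the questionnaire to the subject" (7.4.4.7). The timeline in 7.6.2 and the visit lists in 7.7 agree: Visit 1 has no ICO.
- **Early exit.** For some departures, 5.5 says that "the last visit, in which their withdrawal was determined, will be considered their final visit". The final-visit list in 7.7.3 includes the ICO, eye symptoms and AE evaluation.
- **Unscheduled visits.** Under 7.7.5 these are optional and may be held for AEs or for other reasons. The content specified is that "all pertinent data on the adverse events reported should be collected".
- **Outcomes and analysis.** Stopping for intolerance is not listed in 7.4.1 or 7.4.2. Primary variables are analysed per protocol (10.3.2.1: adherence of at least 80% and completion without deviations). Secondary variables, including the four symptoms, are analysed in everyone with at least one dose (10.3.2.2). Section 10.4.1 adds: "There is no imputation procedure for missing data".

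**The concern.** The trial asks whether PRO-231 is tolerated as well as the comparator. A subject who gives up the drops because they cannot be tolerated answers that question most directly. Stinging, grittiness, itching and tearing are likely forms of such intolerance, and under 7.4.4.3.4 none of them triggers the AE-based follow-up. Whether that subject contributes an ICO then depends on how one sentence in 5.5 is read and on what staff choose to do at the visit.

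Two losses need to be kept apart. Leaving early stoppers out of the per-protocol set can be undone with another analysis set. An ICO that was never collected cannot be recovered. If such subjects are more frequent in one arm, the comparison leans towards no difference, and 10.3.1 interprets a non-significant result as similarity.

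**Working it through.** **1. Does the final-visit sentence in 5.5 close the gap?** As translated it has two readings.

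- *Reading A:* it covers subjects who leave for reasons other than consent withdrawal or major deviation. Intolerance is then included, and the visit where withdrawal is determined becomes the final visit. But the sentence only labels a visit; it does not say that the 7.7.3 procedures are to be done there. If that visit is Visit 1 or an unscheduled one, neither 7.7.2 nor 7.7.5 calls for an ICO. If an ICO is taken, a value from about day 3 carries the label of a visit scheduled for Day 8, which fits poorly with the statement that nothing is imputed.
- *Reading B:* it covers subjects who fail to finish because of consent withdrawal or major deviation. Intolerance is then not named.

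Under neither reading is an ICO clearly required.

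**2. Who is outside the primary ICO analysis even if an ICO is taken?** Planned doses: 3 per day × 7 days = 21. Threshold: 0.80 × 21 = 16.8, so 17 doses are needed. Five full days give 15 doses, so the 17th falls on day 6. Anyone stopping before it is below 80% and excluded.

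**3. Plan's arm size.** 17 × 1.10 = 18.7, rounded up to 19 per arm (10.1.2). This reproduces the inflation step. The point does not rest on how the 17 was obtained.

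**4. How likely is at least one such subject?** The documents give no intolerance rate, so *q* is assumed. P(at least one of 19) = 1 − (1 − q)^19; three or more leaving takes an arm below 17 unless subjects are replaced.

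| Assumed q | P(≥1 of 19) | P(≥3 of 19) |
|---|---|---|
| 2% | 32% | 0.6% |
| 5% | 62% | 6.7% |
| 10% | 86% | 29% |
| 20% | 99% | 76% |

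**5. How much could be hidden?** Suppose k stoppers, all in one arm of 19, have an ICO change D points worse than completers. Leaving them out hides k × D / 19. Both k and D are assumptions.

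| k | D = 20 | D = 30 | D = 40 |
|---|---|---|---|
| 1 | 1.05 | 1.58 | 2.11 |
| 2 | 2.11 | 3.16 | 4.21 |
| 4 | 4.21 | 6.32 | 8.42 |

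**6. What would a direct count show?** Two-sided Fisher exact test on stopping for intolerance: 4/19 v 0/19 gives p = 0.105; 5/19 v 0/19 gives p = 0.046. A count by arm is therefore chiefly descriptive at this size, but it shows an imbalance that no listed outcome reports.

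**7. What would a collected ICO mean?** Annex 16.4 asks about the past week, and dosing starts on day 1. At day 3, at most three of the seven recalled days involve dosing. For someone who stops on day 3 and attends on Day 8, the preceding week (days 1 to 7) again holds at most three dosed days.

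**The case against.** The strongest defence is that much of the information is already captured.

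- Reading A of 5.5 makes the withdrawal visit the final visit, and 7.7.3 puts the ICO in it.
- The four symptoms are asked about since the last visit, at Visit 1 and the final visit, and are a tolerability outcome in all dosed subjects.
- For a subject who cannot be brought in, 5.5 sets AEs and the reason for leaving as minimum data.
- Unscheduled visits are not confined to AEs.
- Elimination need not mean leaving before the final visit: the adherence criterion relies on the bottle's final weight, and the product is returned at that visit.

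These points stand. A reader might infer that intolerance is recorded nowhere, or that such a subject can have no post-dose ICO. The documents do not support either inference. A reader might also infer that all discomfort is barred from AE status. Only ICO change and the four symptoms are barred; hyperemia of grade 3 or more, chemosis and staining of grade III or more are AEs, other complaints such as eye pain are not excluded, and 7.4.4.6 contradicts the bar for three of the four symptoms.

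The defence does not supply a sentence requiring an ICO or later contact after removal for intolerance, nor an outcome that counts such removals. It is also right that collecting an ICO alone would not repair the primary analysis, given steps 2 and 7.

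**Conclusion.** The gap is real but narrower than a total loss of information. Collection of the ICO and further follow-up after removal for intolerance are not clearly required. Sections 5.5, 7.4.4.3.4, 7.4.4.6 and 7.7.3 do not settle the matter between them. Removal for intolerance is not an outcome, and early stoppers are outside the per-protocol ICO analysis. The primary tolerability comparison can therefore miss the least tolerant subjects.

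A lean towards similarity requires more such subjects, or worse ones, in one arm. With equal stopping and equal excess, the discomfort in both arms is understated but no difference is hidden. The magnitude is unknown: the 2 to 20% rates, the 20 to 40 point excess and the 5/19 split are illustrations, and nothing in the documents shows that they will occur. This should be corrected before enrolment, because data not collected cannot be recovered at analysis.

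**What to change.** 1. In 5.2.1 and 5.5, state that elimination does not end data collection unless consent for follow-up is withdrawn. Reconcile 5.5, 7.4.4.3.4, 7.4.4.6 and 7.7.3, so that it is clear which subjects the final-visit sentence covers, which assessments are done, and whether the named symptoms can be AEs.
2. At the visit where removal is decided, collect the final-visit assessments, including ICO and eye symptoms. Code the visit as early termination, with the actual study day and last-dose date, rather than as Day 8. Keep the existing Day 8 visit and Day 12 call for all dosed subjects.
3. Add, as a tolerability outcome, the number who stopped study drug for intolerance or hypersensitivity, by arm, in all dosed subjects. This count carries the repair. Show the ICO in all dosed subjects beside the per-protocol result, noting that past-week recall limits what an early or post-stopping value means.

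The cost is protocol wording, one eCRF visit label and one extra table; the questionnaire, visits and call already exist. The downside is that a few subjects attend Day 8 after stopping, and early ICO values are less comparable with those of completers.

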7.3 Assignment of treatment

The assignment/randomization of the treatment will be carried out centrally using a validated electronic system from an external provider, previously evaluated and authorized by Laboratorios Sophia S.A. de C.V. There are two treatment groups. Participants will be randomized in a 1:1 ratio to treatment with PRO-231 or VIGAMOXI.® Having the same probability of being assigned to one or the other treatment. After signing the FCI, the subject will receive a participant number with which all their information will be encrypted pseudonymity during collection and completely anonymized during analysis. The generation will be carried out by a third party, authorized by Laboratorios Sophia, S.A. de C.V., through its electronic system, through a list of random numbers generated by software (SAS Institute Inc, Cary, NC, USA). The information pertaining to this third party will be on file. Only the principal investigator and the person responsible for the statistical analysis will be blinded, because the primary packaging of the comparator cannot be modified to resemble the product under investigation. Despite this, the secondary packaging for the products will be the same and the researcher will not know the allocation. IP will be identified by means of labels in accordance with current and applicable regulations, which must contain at least:

- Sponsor's name, address, and phone number.
- Dosage form and route of administration.
- Number of doses.
- Batch number.
- Legend "Exclusively for clinical studies".
- Expiration date.

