10.1.2 Size Calculation

PRO-231 ophthalmic solution is expected to be safe in its ophthalmic application as it presents an incidence of AE similar to that presented by VIGAMOXI.®

On this basis, a sample of 17 ophthalmologically and clinically healthy subjects was estimated. This value increased by 10% considering possible losses. Based on this consideration, 19 subjects per arm (38 subjects in total) are required to provide one eye (OD) to respond to the primary objective of the study.

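### The unconditional statement in section 5.5 that loss to follow-up below 20% does not threaten validity is not true for this 38-subject comparison; a two-way sensitivity analysis should replace it

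*Combined protocol and SAP*

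**What the plan says.** Section 5.5 gives the tolerance without qualification: "A loss of follow-up <20% is considered not to be a problem for the validity of the results obtained". It cites two references but does not say whether the percentage applies to the whole trial or to each arm, and it sets no condition on the reason for loss. A lost subject is one who was assigned product, "who at some point were active subjects of the study, but their final evaluation could not be completed". Section 5.5 has the site ask such subjects about adverse events and why they left, but the 20% rule does not use the answers.

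Other sections decide what happens to these subjects:

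- 10.1.2: "a sample of 17 ophthalmologically and clinically healthy subjects was estimated"; "This value increased by 10% considering possible losses"; and so "19 subjects per arm (38 subjects in total) are required".
- 5.2.2: the sponsor may replace subjects who withdraw consent or are lost. This is an option, not a duty.
- 10.3.2.1: the primary variables are analysed per protocol, meaning at least 80% adherence and participation concluded without deviations.
- 10.4.1: "There is no imputation procedure for missing data".
- 10.3.1: p of 0.05 or more, with a 95% CI that includes zero, is read as the two treatments being similar.

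**The concern.** The trial asks whether one eye drop is less safe or less comfortable than another, so a subject who stops coming because the drop is unpleasant carries part of the answer. With 19 per arm, a handful of such subjects can decide a comparison of rare events. The primary set leaves out subjects who do not complete, nothing is filled in for them, and non-significance counts as the favourable finding. Outcomes missing from the PRO-231 arm for reasons linked to the drop would therefore push the result towards similarity. A blanket statement that loss below 20% is harmless gives the final report a ground for not looking into this.

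**Working it through.** **Sample size first.** The comparison is of two proportions, two-sided alpha 0.05, 1:1 allocation, with 50% for PRO-231 (10.1.1). Power and the comparator rate are not stated. I assume 80% power and 6/62 = 0.0968, the count of ocular events over the moxifloxacin arm of the cited study. With unpooled variance:

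n = [0.0968 × 0.9032 + 0.5 × 0.5] × [(1.960 + 0.842)/(0.5 − 0.0968)]² = 16.29, rounded up to 17.

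This matches the plan. Adding 10% gives 17 × 1.1 = 18.7 (or 17/0.9 = 18.9), so 19. The allowance is therefore 19 − 17 = 2 losses per arm. The figures below use only the 19 per arm and do not depend on these assumptions.

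**What passes the 20% rule.**

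- Over the whole trial: 7/38 = 18.4% passes and 8/38 = 21.1% does not. Seven losses leave 31, an average of 15.5 per arm.
- Per arm, if that was meant: 3/19 = 15.8% passes and 4/19 = 21.1% does not.

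**What a passing loss could conceal.** Suppose all losses fall in one arm, no event is observed in either arm, and every lost subject had the event. With k events in one arm of 19 and none in the other, the two-sided Fisher p is 2 × C(19,k)/C(38,k).

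| Lost from one arm | Share of 38 | Observed | If all lost had the event | Fisher p |
|---|---|---|---|---|
| 4 | 10.5% | 0/15 v 0/19 | 4/19 v 0/19 | 2 × 3,876/73,815 = 0.105 |
| 5 | 13.2% | 0/14 v 0/19 | 5/19 v 0/19 | 2 × 11,628/501,942 = 0.046 |
| 7 | 18.4% | 0/12 v 0/19 | 7/19 v 0/19 | 2 × 50,388/12,620,256 = 0.008 |

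Each observed comparison has p = 1.00 and would be read as similar. With one event seen in each arm, 1/12 v 1/19 (p = 1.00) could become 8/19 v 1/19 (p = 0.019).

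The decision rule also needs a 95% CI that excludes zero. For 5/19 v 0/19 the difference is 0.263 and its standard error is √(0.263 × 0.737/19) = 0.101. The simple interval is 0.263 ± 1.96 × 0.101, or 0.065 to 0.461, which excludes zero. The plan does not name a CI method.

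**If the limit is per arm.** Three hidden events alone do not reverse the reading: 2 × C(19,3)/C(38,3) = 2 × 969/8,436 = 0.23. With two events already seen in that arm they can: 2/16 v 0/19 has p = C(16,2)/C(35,2) = 120/595 = 0.20, and three more give 5/19 v 0/19, p = 0.046.

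**What data remain for a lost subject.** Hyperemia, chemosis, visual acuity and staining are assessed on days 3 and 8, and adverse events on days 3, 8 and 12. The Eye Comfort Index is scheduled only at baseline and day 8 (1.3 and 7.6.2). A subject who does not return after day 3 therefore has no change score on the only primary tolerability variable.

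**The case against.** A reader might infer four stronger things, and the documents support none of them.

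- *The 20% contradicts the 10%.* It does not. The 10% is a planning allowance and the 20% a validity tolerance. The power cost is also modest: by the plan's own power formula, and with the assumptions above, an even 16/15 split gives 77% to 79% against 81.7% at 17/17. Replacement under 5.2.2 can restore numbers, although it is optional and cannot recover the outcomes of those who left.
- *The rule is pooled over arms.* That comes from silence. An unqualified percentage reads most naturally as overall, but the text does not say so.
- *Lost subjects simply vanish.* They do not. Day-3 data exist for those who attended. For some early leavers the visit at which withdrawal is determined counts as the final visit. Subjects removed for adverse events are followed to closure, lost subjects are asked about events, and the secondary variables use all dosed subjects with the needed measurements (10.3.2.2). Intolerance of study drug is a separate elimination criterion (5.2.1), so not every such departure need be classed as loss.
- *The sentence itself removes subjects or certifies the result.* It feeds no analysis step. The exclusion comes from the per-protocol set, and deleting the sentence alone would change no estimate.

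It is also fair to say that the examples are extremes. If loss were unrelated to arm, seven losses would all fall in one arm with probability 2 × C(19,7)/C(38,7) = 0.8%, and nothing in the documents predicts loss of that size in a seven-day study of healthy volunteers. What stands is that the rule makes no exception for loss related to arm or to the product, which is the case that matters.

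**Conclusion.** The point holds as a limited but real one. The claim that loss below 20% does not affect validity is false for this trial on the overall reading, where five losses from one arm can be enough to overturn a finding of similarity. On the per-arm reading it is weaker but still not safe. The error runs towards the favourable conclusion, because the primary set omits non-completers, nothing is imputed and non-significance is read as similarity.

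The size rests on worst-case assumptions: all losses in one arm, all with the event, none captured by day-3 visits or questioning. It shows what the rule would accept, not what is likely to happen. The two cited references cannot be seen here, so whether they qualify the 20% is unknown. The protocol does not.

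**What to change.** 1. Delete the 20% sentence in 5.5 and state that the design allows for two losses per arm.
2. Report losses by arm, with day, last dose taken and reason.
3. Add to 10.3.2 a sensitivity analysis in all dosed subjects. For each binary primary safety variable and each ocular symptom, first use day-3 and adverse-event follow-up data. Then count outcomes that are still unknown as events in the PRO-231 arm and non-events in the comparator arm, and then the reverse.
4. For change in the Eye Comfort Index and in visual acuity, add a matching shift (tipping-point) check: how far the missing values in one arm must move before the conclusion changes.
5. Report any finding of similarity that changes under these checks as not robust.

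The cost is a short protocol and SAP edit, a few extra tables and a less favourable stated tolerance for loss. It needs no added subjects or visits. Worst-case counting is deliberately severe, so it should be labelled as a bound beside the main result.
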